- 5) Bilateral DCIS is permitted if non-high grade DCIS is confirmed in both breasts at the time of mammogram and diagnostic biopsy
- 6) Able to give informed consent and comply with the trial schedule and completion of Patient Reported Outcome questionnaires
- 7) Patient fit and willing to undergo surgery
- 8) Written Informed Consent obtained

Exclusion

- 1) Previous or current diagnosis of invasive breast cancer or previous ipsilateral DCIS (previous surgically treated contralateral DCIS is permitted)
- 2) A mass lesion clinically on imaging at the site of the microcalcification which has not been proven on biopsy to be a specific benign lesion
- 3) Surgical procedure with curative intent (even if clear margins have not been achieved)
- 4) Unequivocal comedo necrosis observed
- 5) Any serious and/or unstable pre-existing condition that would prevent compliance with the trial or the consent process
- Recent onset ipsilateral blood-stained nipple discharge without benign explanation
- High risk group for developing breast cancer (as defined in current NICE guidelines for familial breast cancer (42), or due to prior exposure to mantle field radiotherapy)

Central Histopathology Review

All diagnostic histopathology slides will be submitted for central review as follows:

- Prior to randomisation to confirm low risk disease
- Following local confirmation of DCIS grade migration (from subsequent core biopsies in Active Monitoring Arm patients only)

The outcome of the central review will be made available within 1 week of receipt of the slides

Trial Assessments

- Surgery Arm Annual mammography for a minimum of 10 years
 - Patient Reported Outcomes (QoL and Health Economics) for 5 years
 - Collection of follow-up data via annual follow-up appointment for years 1-5 and via annual telephone call to patient for years 6-10

- Active Monitoring Arm Annual mammography for a minimum of 10 years
 - Patient Reported Outcomes (QoL and Health Economics) for 5 years
 - Collection of follow-up data via annual telephone call to patient for 10 years

Radiology Second Opinion Service

A radiological second opinion service is available upon request for Active Monitoring arm patients. The second opinion will be provided within 1 week of the request being made.

Translational Research

The following samples will be collected for translational research:

- Tumour blocks from diagnostic biopsies (all patients)

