- Tumour blocks from surgical resection specimen (Surgery Arm patients)
- Tumour blocks from surgical resection specimen following disease progression (all patients)

Trial Duration

Recruitment 6 years (2 years Feasibility Study plus 4 years main trial)

Follow-up 10 years (extended follow-up data to be obtained via the Data Linkage Service)

Version 4.0, 15th March 2016 Page viii

CONTACT DETAILS

LORIS Trial Office

Cancer Research UK Clinical Trials Unit (CRCTU), Institute of Cancer and Genomic Sciences, University of Birmingham, [name]

★ [contact]
★ [contact]
★ [contact]

Quality of Life Coordinating Centre

Sussex Health Outcomes, Research & Education in Cancer (SHORE-C), Brighton and Sussex, Medical School, University of Sussex, [name]

[figure not shown]
Translational Coordinating Centre

Biomarkers and Companion Diagnostics, Edinburgh Cancer Research Centre, University of Edinburgh, Western General Hospital, [name]

★ [contact]
★ [contact]
★ [contact]

Trial Schema

Page x Version 4.0, 15th March 2016

Schedule of Events:		Pre-Randomisation			On Stu	Long Term Follow-Up	
Event	Screening		Study Entry	Po	ost-Randomisation	Annual Follow-up Years 1 - 5	Annual Follow-Up Years 6-10
Local diagnosis of non-high grade DCIS (small volume biopsy plus VACB, or first line VACB, or small volume biopsy or VACB plus open diagnostic surgical biopsy without clear margins or open diagnostic surgical biopsy without clear margins (alone)	Х						
Medical history	Х						
Confirmation of eligibility	Х			:			
Informed consent for registration	Х			diagnosis			
Registration	Х			diag			
All diagnostic slides submitted for Central Histopathology Review	Х	Review		s of			
Informed consent for randomisation			Х	days			
Patient completes baseline QoL questionnaires and Accept/Decline questionnaire ⁵		Histopathology	Х	09 u			
Randomisation		atho	Х	within			
Baseline details		stop			Х		
Treatment				surgery	Х		
Endocrine therapy/radiotherapy initiated in accordance with local practice		Central			^		
Primary tumour sample collection Diagnostic biopsy (all patients) Surgical specimen (Surgery Arm patients only)		on		undergo	Х		
Patient Reported Outcomes		Jae H		Arm			
QoL questionnaires at: 3 months, 6 months and annually Patient Costs Questionnaire at 1 random time point		confirmed		Surgery A	X	Χ	
Annual follow-up Mammography (all patients)		CIS		Sur		X	X

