8 QUALITY OF LIFE

8.1 Quality of Life

The primary QoL aspect of the trial examines the hypothesis that the psychological well-being of women in the Active Monitoring arm is non-inferior to that associated with standard surgical and adjuvant treatments. In addition, these QoL outcomes will inform future patients diagnosed with low risk DCIS when making decisions about their treatment options. Patients will be asked to complete questionnaires at different time points (see Table 1 Timeline of Quality of Life Questionnaires, later in this section) that will look at factors that may influence:

- Decision to join or reject the trial using the Accept/Decline questionnaire (Feasibility Study only)
- Psychological adjustment anxiety trait and ways of coping. Using the Speilberger State-Trait Anxiety Inventory (STAI) and Brief ways of coping questionnaire (baseline only)

In addition, the impact that either Surgery or Active Monitoring may have on anxiety state and general well-being is measured using:-

- STAI
- SF-36v2 Health Survey

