8.1.5 Euro Qol EQ-5D (EQ-5D)

The EQ-5D is a health status measure comprised of 5 attributes or dimensions; mobility, self-care, usual activity, pain/discomfort, and anxiety/depression. The single summary scores derived from the EQ-5D will be used in QALY analyses and in cost-effectiveness and cost-utility analyses.

Page **25** of **48** Version 4.0, 15th March 2016

Table 1. Timeline for Quality of Life Questionnaires

	Time points (months)							
Questionnaire	Baseline	3	6	12	24	36	48	60
Accept/Decline (Feasibility Study only)	х							
Brief COPE	х							
STAI Trait Anxiety	Х							
STAI State Anxiety	Х	Х	Х	Х	Х	Х	Х	Х
SF-36v2 Health Survey	Х	Х	Х	Х	Х	Х	Х	Х
EuroQol EQ-5D	Х	Х	Х	Х	Х	Х	Х	Х

With the exception of the baseline QoL questionnaires that are completed by the patient prior to randomisation, all other questionnaires will be distributed directly to the patients' home address by SHORE-C, for completion at the designated time points. A member of the SHORE-C team may contact the patient if the questionnaires that have not been returned or have not been completed fully.

The site research team should inform SHORE-C of any changes to the patients address or telephone number by completing the Change of Contact Details Form. Note that changes to patient address and telephone details will be maintained by SHORE-C only and should not be provided to the Trial Office.

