16.2.2 Analysis of Outcome Measures

The primary research question to be addressed by this analysis asks if active monitoring for newly diagnosed, asymptomatic, low grade DCIS is non-inferior in terms of ipsilateral invasive breast cancer survival time when compared to surgical intervention to remove all traces of DCIS at diagnosis.

The primary aim is to test the null hypothesis that active monitoring of women diagnosed with low risk DCIS is not non-inferior in terms of invasive breast cancer free survival time compared to treatment with surgery. Invasive breast cancer survival time will be compared across the two arms on a per protocol and intent-to-treat basis, using a 1-sided (5% significance level) log-rank test for non-inferiority and a hazard ratio with a one-sided 95% confidence interval.

There is very little relevant evidence of the actual ipsilateral invasive breast cancer rate amongst low risk DCIS patients and an event rate of 2.5% at 5 years reflects current evidence (26). A difference in invasive breast cancer survival of no more than 2.5% is judged as clinically acceptable both by the TMG and the wider breast cancer clinical community. This gives a non-inferiority margin for the trial defined as an absolute reduction in the 5 year ipsilateral invasive breast cancer free survival rate at 5 years of 2.5% i.e. from 97.5% to 95% and this equates to a hazard ratio of HR=2.02 . Models for survival data will be considered to take into account the stratification factors and other potentially important prognostic factors.

All analyses will be carried out for both per protocol and intent to treat study populations. The primary and secondary outcomes will be calculated for all patients and compared between treatment groups. Time to event outcomes will be calculated for all patients and methods described by Kaplan and Meier used to present survival curves. The log-rank statistic will be used to test hypotheses.

Results from the Brief COPE will allow us to dichotomise women into two groups, those who manage a situation using a problem focused approach and those who have a detached method of coping.

The STAI permits us to measure changes in state anxiety over time. We will examine changes using Analysis of Covariance (ANCOVA) with baseline trait and state anxiety as covariates.

Page **35** of **48** Version 4.0, 15th March 2016

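### State anxiety is collected at seven time points after baseline but is to be analysed by ANCOVA, which can bias the arm difference in either direction if anxiety-related non-return differs between arms

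*Protocol*

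**What the plan says.** Section 16.2.2 of the protocol introduces the instrument with "The STAI permits us to measure changes in state anxiety over time" and goes straight on to the method: "We will examine changes using Analysis of Covariance (ANCOVA) with baseline trait and state anxiety as covariates". No other analysis of state anxiety is named.

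The Schedule of Events gives "QoL questionnaires at: 3 months, 6 months and annually". Table 1 in section 8.1.5 marks STAI State Anxiety at baseline and at 3, 6, 12, 24, 36, 48 and 60 months, so there are seven scores per woman after baseline. Trait anxiety is taken at baseline only. After baseline the forms are sent to the home address. On non-return, section 8.1.5 says: "A member of the SHORE-C team may contact the patient if the questionnaires that have not been returned or have not been completed fully".

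Section 8.1 sets out the hypothesis that the "psychological well-being of women in the Active Monitoring arm is non-inferior to that associated with standard surgical and adjuvant treatments". Psychological well-being is also part of the overall aim in section 2.2.1 and of the trial question in section 3.

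**The concern.** ANCOVA in its usual form takes one outcome per woman. Applied at a given time point, it uses the women who returned that form, their baseline scores and nothing else. A woman whose score rose at 12 and 24 months and who then stopped replying contributes nothing to the 36-, 48- or 60-month comparison, although her observed scores say something about where she was heading.

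This matters if the tendency of anxious women to stop replying differs between arms. The allocation is surgery or no surgery, so women know their arm. Routine contact also differs: sections 7.1.3 and 7.2.3 expect an annual clinic visit for most Surgery patients and an annual telephone call for Active Monitoring patients. Unequal loss is therefore possible, though the protocol does not predict it in either direction. For a non-inferiority hypothesis, a bias that shrinks a detriment is the dangerous one, because it favours the conclusion being sought.

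**Working it through.** **Plan's own figures.** The protocol gives no SD, sample size or questionnaire loss rate for state anxiety, so there is no stated figure to reproduce. Its 50 events and 932 women belong to the primary outcome. The only loss figure, 10% in section 16.2.6, covers loss to follow-up and non-adherence for that outcome. From the document come 932/2 = 466 women per arm and seven post-baseline time points. Everything else below is assumed.

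**Why bias arises.** At time point t the model is Y_t = a + d·arm + b·baseline + e, fitted to women with Y_t observed. The bias in d is roughly the mean of e among responders under Active Monitoring minus the mean of e among responders under Surgery. If loss depends on the previous score, e is shifted among responders. If the shift is the same in both arms it largely cancels; otherwise it does not.

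**Simulation 1.** Assumptions:
- True detriment 0.15 SD at every time point.
- Correlation 0.35 + 0.30·exp(−gap/24 months), which is about 0.61 at a 3-month gap and 0.37 at 60 months.
- Women who stop replying do not return.
- In the one-sided cases, the odds of loss in one arm rise 1.5-fold or 2-fold per SD of the last score.

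Completer ANCOVA at 60 months:

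| Loss by 60 months | Anxiety-related loss in | 1.5-fold | 2-fold |
|---|---|---|---|
| 10% | Active Monitoring only | 0.140 | 0.135 |
| 20% | Active Monitoring only | 0.127 | 0.116 |
| 36% | Active Monitoring only | 0.117 | 0.082 |
| 36% | both arms, same rule | 0.151 | 0.143 |
| 36% | Surgery only | 0.185 | not run |

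Understatement with such loss in Active Monitoring only:
- 10% loss: (0.150 − 0.140)/0.150 = 7% and (0.150 − 0.135)/0.150 = 10%.
- 20% loss: 15% and 23%.
- 36% loss: 22% and 45%.

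Two re-runs of the 36% Active Monitoring case gave 0.114 and 0.116 (1.5-fold) and 0.077 and 0.086 (2-fold). With random loss the ANCOVA was unbiased (0.147 in one re-run). A likelihood analysis using all observed scores gave 0.153 and 0.149 in the two 36% Active Monitoring cases.

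**Simulation 2.** True detriment 0.30 SD; exchangeable correlation 0.5 or 0.7, or autoregressive 0.8; log-odds of loss rising by 0.7 per SD, and exp(0.7) = 2.01, so about 2-fold; loss 10–40%. The ANCOVA adjusted for baseline state anxiety only. Its results at 60 months:
- Random loss: 0.29–0.31.
- Same rule in both arms: 0.28–0.30.
- Active Monitoring only: 0.28–0.29 at 10% loss, 0.23–0.27 at 20%, 0.17–0.24 at 40%.
- Surgery only: 0.32 at 10%, 0.33–0.36 at 20%, 0.37–0.40 at 40%.

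The analysis using all intermediate scores gave 0.29–0.31 throughout.

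The percentages depend on the assumed detriment. In absolute terms, the understatement in simulation 1 runs from 0.150 − 0.140 = 0.010 SD to 0.150 − 0.082 = 0.068 SD.

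**The case against.** The strongest reply is that the protocol does not fix the analysis just simulated. It does not say one value per woman, completers only, or which time point, and its reference to change over time could describe an ANCOVA with time as a repeated factor. The form of the model and the handling of missing forms may be in a statistical analysis plan that is not shown. This stands in part: silence on those details is no fault. But ANCOVA is stated, and it is the only method stated. If a likelihood-based repeated-measures model is meant, the change below is a clarification; a classical repeated-measures ANCOVA would drop every woman with a gap.

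A reader might infer that harm under Active Monitoring will be understated. The documents do not support that. It requires anxiety-related loss that is stronger in that arm, which nothing in the protocol establishes. The reverse pattern exaggerates the detriment, and a common pattern does little.

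A reader might also infer that scores before dropout are never used, or that seven separate 5% tests are planned with an inflated false-positive rate. If ANCOVA is run at every time point, each score does count at its own time point; if it is run once, there are not seven tests. The protocol sets neither seven tests nor a 5% level for anxiety, and false-positive and power figures for detecting a difference do not fit a non-inferiority hypothesis.

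The size is also open. Section 8.1.5 allows non-responders to be contacted, which may keep loss low.

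**Conclusion.** The point holds as a choice of method. For an outcome measured seven times after baseline, and tied to the trial's main question, the stated ANCOVA is open to bias when anxiety-related non-return differs between arms. The direction is not known in advance. Only with such loss in Active Monitoring alone does the 60-month understatement reach about 7–10% at 10% loss and 22–45% at 36% loss. Those figures rest on an assumed 0.15 SD detriment, assumed correlations and assumed dropout odds, none of them in the protocol. The case for change does not depend on the direction: an analysis using all observed scores was close to unbiased in every scenario in which it was run.

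**What to change.** In section 16.2.2, replace the ANCOVA sentence with one mixed model for repeated measures on all post-baseline state-anxiety scores. Its terms are arm, time point, arm by time point, baseline state anxiety by time point and baseline trait anxiety, with unstructured covariance. It includes every woman with at least one post-baseline score. Report the arm difference with a confidence interval at each time point.

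The sponsor should state in advance which contrast leads: a named time point or the average over time. The average can dilute a detriment confined to early or late follow-up, so this choice of estimand should be made deliberately. Add a sensitivity analysis for loss that the observed scores do not explain.

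The cost is wording and slightly more modelling, with no new data or covariates. The main model still assumes that loss is explained by the observed scores, which is why the sensitivity analysis is needed.

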16.2.3 Planned Sub Group Analyses

Treatment efficacy will be investigated descriptively for subgroups of patients included as stratification factors: age, overall maximum diameter of microcalcification, surgical intent, detection method and intent to prescribe anti-oestrogen therapy.

16.2.4 Planned Interim Analysis

The primary and secondary outcomes will be analysed descriptively and presented to an independent DMC annually, along with information relating to trial recruitment and conduct, data completeness, treatment compliance and safety (see Section 17.6 Data Monitoring Committee).

16.2.5 Planned Final Analyses

The study will complete recruitment within 6 years and the analysis will take place when all patients have been followed-up for at least 5 years. Patients will continue with mammographic follow-up for a minimum of a further 5 and additional analysis will be undertaken.

16.2.6 Sample Size Justification

The sample size calculation is based on the primary outcome of ipsilateral invasive breast cancer survival time. The primary analysis will be a comparison of the ipsilateral invasive breast cancer free rate between the Active Monitoring arm and Surgery Arm using a log-rank test for non-inferiority. The justification for the sample size is explained below.

Taking into account all published 5 year recurrence rates post-surgery for low risk disease, excluding contralateral disease and ipsilateral *in situ* disease, the projected recurrence rate (ipsilateral invasive breast cancer rate) at 5 years in the Surgery Arm is 2.5%. There is no relevant published data on 5 year ipsilateral invasive cancer rate in non-operated asymptomatic mammogram-detected low risk DCIS diagnosed by VACB and centrally reviewed. We have therefore based our non-inferiority calculation on extrapolation from the surgical data, estimates of overtreatment and what is judged to be a clinically relevant non-inferiority margin.

Page **36** of **48** Version 4.0, 15th March 2016

The non-inferiority design aims to show that not treating low risk DCIS with surgery is no worse (than a given margin) than treating with surgery. The primary outcome is ipsilateral invasive breast cancer free survival time and we will use a log-rank test for non-inferiority to determine whether no surgery is as good as surgery in these low risk DCIS patients by comparing the survival distributions of the two treatment groups. Because of the directional nature of the hypothesis, this non-inferiority test is one-sided. Jung *et al.* (49) derived an asymptotically exact sample size formula for the non-inferiority log-rank test to give the number of patients required to reject the null hypothesis that no surgery is worse than surgery, based on a given level of power and significance, assuming exponential survival distributions for both treatment groups, uniform patient accrual during a specified accrual period and set number of events during a period of follow-up, uniform censoring and no loss to follow-up.

The one-sided Type I error rate is set at 5% and Type II error rate set at 20%, giving 80% power. The accrual period will be over 6 years and patients will be in follow-up for 5 years. The ipsilateral invasive breast cancer free rate at 5 years, based upon previous data (see above), is estimated to be 97.5%. The non-inferiority margin of maximal difference is determined to be 2.5%, therefore if the invasive breast cancer free rate at 5 years in the untreated group is not worse than 95%, then non-inferiority would be concluded since it falls within 2.5% of the treated population's invasive breast cancer free survival rate (97.5%). This decision was reached by the TMG, which comprises clinicians and patient representatives as well as statisticians. This non-inferiority margin equates to a hazard ratio of 2.02

The sample size calculation, given the above information estimates that 50 events will be sufficient to answer robustly the primary research question and it is estimated that 932 patients are required to achieve this number of events allowing for a 10% loss to follow-up/non-adherence rate.

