15 END OF TRIAL DEFINITION

For the purposes of REC approval, the end of trial date is deemed to be 6 months after the date of last data capture or the final analysis of predictive biomarkers, whichever is later. This will allow sufficient time for the completion of protocol procedures, data collection and data input.

The duration of time for which patient follow-up data will be collected is dependent on future funding arrangements. Current funding is secured for this to continue for 10 years after the start of the trial, and further funding will be sought for this to continue long term.

The LORIS Trial Office will notify the REC that the trial has ended and a summary of the clinical trial report will be submitted to the REC within 12 months of the end of trial.

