16.1.4 Planned Final Analysis

Assessment of the progression criteria will take place at the end of the twenty-fourth month of the Feasibility Study. Success in the progression criteria would demonstrate how the main trial can achieve the targeted recruitment and robustly answer the main trial objectives as detailed below. If the progression criteria are met, the trial will proceed, and will initiate at least 60 sites and will recruit for an additional 4 years to achieve the target of 932 patients.

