16.1.5 Specific Progression Criteria from Feasibility Study to Main Trial

- 20 sites trained, open and recruiting by the end of year 2
- 60 patients randomised by the end of year 2
- · Mean monthly recruitment of at least 6 patients in the last 4 months, as defined above

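### The 50 events and 80% power rest on uniform accrual, while the plan's own staged recruitment, with criteria just met, gives about 43–45 events and 74–76% in the same model at year 11

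*Protocol*

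**What the plan says.** - **Accrual assumption (16.2.6).** The non-inferiority log-rank calculation assumes "uniform patient accrual during a specified accrual period". On timing: "The accrual period will be over 6 years and patients will be in follow-up for 5 years". With a one-sided 5% level, 80% power and a hazard-ratio margin of 2.02, this yields 50 events and 932 women, with 10% allowed for loss or non-adherence.
- **Recruitment plan (16.1.4–16.1.5).** The feasibility phase passes with 20 sites, "60 patients randomised by the end of year 2", and a mean of at least 6 women a month over months 21–24. The trial then "will initiate at least 60 sites and will recruit for an additional 4 years to achieve the target of 932 patients".
- **Analysis trigger (16.2.5).** "the analysis will take place when all patients have been followed-up for at least 5 years". No event count is required.
- **Data collection (section 15).** "Current funding is secured for this to continue for 10 years after the start of the trial", and further funding is to be sought.
- **Endpoint (2.2.2.1).** The primary outcome counts death from any cause as well as ipsilateral invasive cancer. The 2.5% rate behind the sample size (16.2.6) is a rate of ipsilateral invasive cancer only.

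**The concern.** A log-rank test draws its power from events, and at hazards this low events are nearly proportional to person-years. Uniform accrual puts a third of the women in by year 2 and gives a mean follow-up of 8.0 years at year 11. A feasibility phase that passes with 60 women puts 6% of them in by then, so most women enter late and contribute less follow-up by the same date.

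Because 16.2.5 waits for follow-up time and not for events, the lost person-time is never made up before the single non-inferiority test. In addition, 6 years of accrual plus 5 of follow-up places that test at about year 11, one year beyond the secured data collection. At stake is whether the stated 50 events and 80% power follow from the plan's own recruitment design.

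**Working it through.** **Inputs.** All are from 16.2.6 unless noted: 5-year event-free rate 97.5% under surgery; margin HR 2.02; one-sided 5%, 80% power; 932 women less 10% = 838.8 effective, split 1:1 (section 3); accrual over years 0–6; analysis at year 11. Exponential times, as the plan assumes.

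**Formulas**
- Hazards: surgery −ln(0.975)/5 = 0.00506 a year; monitoring 2.02 × 0.00506 = 0.01023 a year.
- Required events: d = 4(1.645 + 0.842)² / ln(2.02)² = 50.0.
- Expected events: 0.9 × 932/2 × (p0 + p1) = 419.4 × (p0 + p1), where p0 and p1 are the event probabilities averaged over entry times.
- Power: Φ(√d × ln(2.02)/2 − 1.645).

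**Step 1: reproduce the plan.** Under uniform accrual, follow-up at year 11 runs evenly from 5 to 11 years, so p0 = 0.0397 and p1 = 0.0784. Events = 419.4 × 0.1181 = 49.5 and power = 79.6%. The stated figures reproduce. They need both uniform accrual and a year-11 analysis, and they place monitoring at the margin rate. Uniform accrual implies 932 × 2/6 ≈ 311 women by year 2.

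**Step 2: staged accrual with the criteria just met.** Take 36 women in months 1–20 and 24 in months 21–24 (6 a month), leaving 932 − 60 = 872 for years 2–6. Three shapes for the last 4 years:
- constant: 872/48 = 18.2 a month;
- 12-month linear ramp from 6 a month to r, where 36 + 6r + 36r = 872, so r = 19.9;
- 24-month ramp, where 72 + 12r + 24r = 872, so r = 22.2.

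| Accrual | Mean follow-up at year 11 (years) | p0 + p1 | Events | Power | Year when 50 events are reached |
|---|---|---|---|---|---|
| Uniform | 8.0 | 0.1181 | 49.5 | 79.6% | 11.1 |
| 60, then constant | 7.2 | 0.1064 | 44.6 | 75.9% | 11.9 |
| 60, 12-month ramp | 7.0 | 0.1042 | 43.7 | 75.2% | 12.0–12.1 |
| 60, 24-month ramp | 6.9 | 0.1024 | 42.9 | 74.5% | 12.2 |

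**Step 3: more women by year 2.** With flat accrual within each phase, at year 11: 120 women give 45.9 events (76.9%), 200 give 47.4 (78.1%), 250 give 48.4 (78.8%), and 311 give 49.5 (79.6%).

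**Step 4: is 60 consistent with the target?** Six a month from 20 sites scales to 18 a month from 60 sites, and 60 + 48 × 18 = 924, close to 932. The progression criteria and the site plan therefore fit together as a recruitment path to 932, and that path is not uniform.

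**Step 5: timing.** Year 6 + 5 = year 11, against secured data collection to year 10. Women randomised in year 6 number about 932/6 = 155 (uniform) or 872/4 = 218 (60, then constant). None of them would have 5 years of data at year 10.

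**The case against.** **Sixty is a pass mark, not a forecast.** This stands. The protocol gives no month-by-month projection, and more than 60 women by year 2 shrinks the loss, as step 3 shows. But only about 311, five times the pass mark, removes it, and tripling the sites after year 2 implies slower early recruitment.

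**Deaths are primary events.** A reader might infer that the trial will fall short of 50 events on its defined endpoint, or that 932 should be replaced by a larger number. The documents support neither. They give no death rate, but a constant hazard of only about 0.1% a year in both arms (an assumption) would bring the constant-rate profile back to 50 events at year 11, and 0.2% would give about 54–56 across the constant and 24-month-ramp profiles. What remains is that 16.2.6 derives 50 and 932 from the cancer rate alone, and that calculation does not hold under staged accrual.

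**Year 10 is not a planned cutoff.** A reader might compute events at year 10 (about 37–39, power 69–71%) and take them as the trial's result. Section 15 describes a funding horizon with more to be sought, 16.2.5 schedules no year-10 test, and the synopsis and section 19 already foresee data linkage and registry tracing. Only the unreconciled timing stands.

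**Accrual is the smaller driver.** True. If both arms had the surgery rate, the model gives 33.3 events (64.9%) under uniform accrual and 28.8–29.9 (59.5–61.0%) under staged accrual. The accrual loss is again about 4–5 points, on top of a larger loss that is a separate matter.

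**Conclusion.** The point holds as an inconsistency between the stated calculation and the stated recruitment plan. There is no arithmetic slip: 50 events and 932 women reproduce on the plan's inputs. With the progression criteria just met, the same model gives about 43–45 events and 74–76% power at year 11, a loss of about 4–5 points. With about 200 women by year 2 it gives about 47 events and 78%.

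This rests on exponential times, monitoring at the margin rate, 10% loss applied as a flat reduction, ipsilateral invasive cancers only, and the recruitment shapes above. It does not show that the composite endpoint will lack events. Two further gaps are plain from the text: the trigger has no event condition, and secured data collection ends about a year before the primary analysis is due. The effect is modest and cheap to correct.

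**What to change.** 1. **16.2.6:** replace uniform accrual with the planned staged profile (feasibility threshold, then opening to at least 60 sites). Restate the expected events and power at the planned analysis, and say whether deaths are counted.
2. **16.2.5:** trigger the primary analysis at the later of 5 years' follow-up for all women and 50 events of the type used in 16.2.6. Set a latest date within the scheduled 10-year follow-up. If that date comes first, report the power for the events then observed.
3. **Section 15:** reconcile the data-collection horizon with that timing, for example by naming the Data Linkage Service (synopsis) and registry tracing (section 19) as the source of primary events after year 10.

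**Cost.** Wording and a rerun of the calculation, with no extra women. Each woman already has annual mammography scheduled to year 10. The downside is a slightly lower stated power, or a primary analysis about a year later on the plan's event rates (about year 11.9–12.2), and later still, up to the latest date, if the true rate under monitoring is lower.
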